3.1.3 Randomization and Blinding

Following the results of the baseline survey, clusters will be randomized in a 3:3:1 ratio, with 27 clusters randomized to receive a campaign with the full dose, 27 clusters randomized to receive a campaign with the fractional dose and 9 clusters randomized to the control arm. Randomization will be stratified by proximity to nearest health center (<5 km vs ≥5 km). In the event of significant imbalance in carriage of VT pneumococci between clusters in the baseline survey, randomization will also be stratified by baseline prevalence, after a decision by the trial steering committee. An equal or proportional number of clusters will be randomized to each study arm from each stratum. The study statistician randomization will prepare the material to generate the list (blocked randomization with fixed block size if only one stratum, by minimisation if more than one stratum), and the final list will be generated by an independent statistician who has no contact with study participants. Study implementation will be blinded to the extent possible. Vaccination nurses will not be blinded to the vaccine they are giving, but they will not communicate vaccine allocation to other members of the team or to participating villages. Villages randomized to the control arm will not receive any “dummy” intervention, so will not be blinded to their group allocation. The trial will be observer-blind in that personnel at KWTRP will be blinded to group allocation until after the completion of culture and serotyping in each survey.

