4.1 Timing of Analysis

Determining whether mass campaigns with fractional dose PCV10 would accelerate herd protection against pneumococcal transmission in Sub-Saharan Africa

The primary endpoint will be the change from baseline in VT carriage at 6 months post-vaccination campaign. The reduction in VT carriage will be calculated by comparing the proportion of children carrying VT pneumococci 6 months post-vaccination to the baseline.

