4.3 Statistical Analysis

All results will be displayed by intervention group (full dose, fractional dose or control).

Descriptions of the study population will be provided at the individual level and at the cluster level as appropriate. Statistical analyses to demonstrate superiority and non-inferiority will be performed at the individual level. Non inferiority will be tested if the superiority of the full dose is shown; therefore, no adjustment for multiplicity is necessary.

Comparison between groups will be done at the cluster level using Student's t-test for continuous variables and Chi square test (or Fisher's exact test if more appropriate) for categorical variable.

Safety analysis will be done at the individual level only, and comparison for categorical variables will be done using a Chi square test (or Fisher's exact test if more appropriate). All comparisons will be done at the 0.05 significance level.

Prevalence of carriage will be presented with a 2 sided 95% confidence interval.

All statistical analysis will be performed on the statistical software Stata version 17 or later.

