4.3.2 Primary Analysis

4.3.2.1 Primary Analysis

The primary analysis is the test of the superiority of the full dose vaccination arm compared to the control arm, on the reduction in NP carriage. The reduction will be calculated by comparing the proportion of children carrying VT pneumococci 6 months post-vaccination to baseline, at the time of vaccination.

This primary analysis on the primary endpoint will be performed on the intent to treat population, using generalised estimating equations (GEE) to estimate risk differences and their associated 95% CI for the effect of the full dose vaccination on the reduction in VT carriage compared to the fractional dose. GEE will be used to account for clustering effect. Adjusted analyses with covariates (including but not limited to age, sex, vaccination coverage, time between baseline survey and vaccination, time between vaccination and follow-up survey, baseline prevalence of VT carriage) and stratification factor will be performed.

The administrative vaccination coverage for each site where vaccination campaign is performed, is obtained by the formula:

(number of vaccinees/number of expected children from the age group 1-9 years old) x 100.

The superiority will be tested at the 0.05 significance level.

For the non-inferiority analysis, the 95%CI around the risk difference in the proportion of children with VT carriage (full dose group – fractional dose group) will be using generalised estimating equations (GEE) and non-inferiority will be achieved if the lower limit of this 95%CI is >-7.5%.

Non inferiority analyses will be repeated on the per protocol population. Sensitivity analyses on the primary endpoint will be repeated by analyzing clusters according to the intervention they actually received if misallocation occurred.

In order to account for any potential seasonal variation seen due to timing of the surveys, additional sensitivity analyses will be performed, comparing the difference in prevalence between the full-dose and control arms, relatively to the reduction observed in the control group..

Multivariable logistic regression analyses will be performed to obtain adjusted estimates of risk factors for VT carriage at baseline and after vaccination campaign. The Odds Ratio and 95% CI will be adjusted for age and sex. Robust SE will be used to allow for clustering at the cluster level. 4.3.2.2 Secondary Analysis.

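### The primary GEE for full dose versus control (27 v 9 clusters) names no variance estimator, degrees of freedom or small-sample correction; an uncorrected sandwich would run at about 8% instead of 5%

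*Combined protocol and SAP*

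**What the plan says.** SAP 4.3.2.1 names full dose versus control as the primary analysis and estimates risk differences with 95% CIs by GEE: "GEE will be used to account for clustering effect". It adds: "The superiority will be tested at the 0.05 significance level". SAP 3.1.2 treats this 5% as two-sided. SAP 4.1 defines the outcome contrast: "The primary endpoint will be the change from baseline in VT carriage at 6 months post-vaccination campaign".

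SAP 3.1.3 allocates 27 clusters to full dose, 27 to fractional dose and "9 clusters randomized to the control arm". It also states: "Randomization will be stratified by proximity to nearest health center". The list is generated "by minimisation if more than one stratum". The stratification factor appears in the analysis only among adjusted analyses, in a list ending "baseline prevalence of VT carriage) and stratification factor will be performed".

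SAP 4.3 makes this test the gate: "Non inferiority will be tested if the superiority of the full dose is shown; therefore, no adjustment for multiplicity is necessary".

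Nothing elsewhere supplies the missing detail. Robust standard errors are named once, at the end of SAP 4.3.2.1, for the risk-factor logistic models. The Student's t-test in SAP 4.3 is for cluster-level group comparisons, and the same section places the superiority and non-inferiority tests at the individual level. Protocol section 12 gives a chi-square test adjusted for clustering, with no degrees of freedom. Stata is named without options.

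The sentence that introduces the GEE names the fractional dose as comparator, although the paragraph opens with full dose versus control. I read the contrast as full dose versus control.

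**The concern.** The ordinary GEE sandwich variance is a large-sample estimator. It is biased downwards when clusters are few, and a normal cut-off ignores how poorly the variance itself is estimated. Both faults are governed by the smaller arm, here 9 clusters. A plain large-sample GEE would fit the text as written and would miss both the stated 0.05 level and the nominal 95% coverage. This matters because the test is the first confirmatory step and its interval would be reported as the effect of a full-dose campaign.

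**Working it through.** **Inputs from the documents.** Control prevalence 30%, full-dose prevalence 15%, ICC 0.02, 36 children per cluster, 20% refusal or absence (SAP 3.1.2); 27 and 9 clusters (SAP 3.1.3); two-sided 5%.

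**Assumptions not in the documents.** The correlation r of cluster prevalence between the two surveys, the split of clusters by distance, and the size of any distance effect. I also use 29 children per cluster as a lower case, from 36 × 0.8 = 28.8.

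**The plan's own figures reproduce.**
- Superiority, 9 v 9 clusters of 30: design effect 1 + 29 × 0.02 = 1.58; effective n per arm 270/1.58 = 170.9; power for 30% v 15% is 91.7%, against the stated 90%.
- Non-inferiority, 27 v 27 clusters of 36: design effect 1.70; effective n 972/1.70 = 571.8; SE = √(2 × 0.15 × 0.85/571.8) = 0.0211; power = Φ(0.075/0.0211 − 1.96) = 94.4%, against at least 90%.

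These are calculations on prevalence with a normal reference. They do not address how the GEE variance is estimated.

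**Error of an uncorrected sandwich.** With equal cluster sizes and no covariates, the GEE contrast is a difference between mean cluster values (prevalence or change). Let σ² be the variance of a cluster value, equal in both arms under the null.
- True variance: σ²(1/27 + 1/9) = 0.1481σ².
- Expected sandwich variance: σ²(26/27² + 8/9²) = 0.1344σ².
- Ratio: 0.907, so the variance is about 9% too small.
- Satterthwaite df: 0.1344² / [(26/729)²/26 + (8/81)²/8] = 14.2.
- Two-sided error: P(|t₁₄.₂| > 1.96 × √0.907 = 1.867) = 8.3%.

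The same steps for 27 v 27 give a ratio of 0.963, 52 df and 6.0% two-sided, or 3.0% one-sided against 2.5%.

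**Simulation under the null.**

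| Setting | Sandwich with 1.96, two-sided error |
|---|---|
| Change from baseline, no stratification (100,000 runs per setting; ICC 0.01 to 0.05; 29 or 36 per cluster; r 0 to 1) | 8.0% to 8.3% |
| The same, in the direction favouring vaccine | 3.9% to 4.2% (target 2.5%) |
| Change, stratified by distance, distance left out (20,000 runs; 35/28 split assumed) | 8.0% |
| The same, distance in the model | 8.4% to 8.6% |
| Change, minimised on distance, stable gap of 0 to 10 points (40,000 runs), distance left out / in | 7.9% to 8.4% / 8.3% to 8.9% |
| Distance also shifts the change by ±5 points, distance left out / in | about 6% / 8.4% |
| Individual-level exchangeable GEE, two surveys (2,800 runs) | 7.9% |

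Model-based standard errors are not a safe default either. In a fitted two-survey exchangeable GEE at r = 0.5 they gave 8.5%.

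**Coverage.** At 30% v 15% and ICC 0.02, the nominal 95% CI covered 91.2% to 91.7% with the uncorrected sandwich and 94.5% to 94.9% with Mancl-DeRouen and t on 34 df.

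**Error after correction.** Mancl-DeRouen with t₃₄ gave 5.0% without covariates under distance stratification, and 4.5% to 4.8% with distance in the model. Kauermann-Carroll with Satterthwaite df gave 4.6% to 5.1% with distance in the model. Kauermann-Carroll with t₃₄ still gave about 6%, so the degrees of freedom must be stated along with the estimator.

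**The case against.** The strongest reply is that the SAP never chooses an uncorrected sandwich, so the 8% belongs to one reading of it. That stands: the figure is conditional, and a corrected estimator would also be consistent with the text. But the plan neither excludes the uncorrected version nor fixes any other.

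A reader might infer that a liberal gate undermines the no-multiplicity argument in SAP 4.3. It does not. Non-inferiority must still pass its own test. In 200,000 simulated trials on follow-up prevalence, with full dose equal to control and fractional dose worse by 7.5 points, the gate opened wrongly in vaccine's favour in 3.7% of trials and a false non-inferiority claim followed in 0.01%. At 30%, 15% and 22.5% (control, full, fractional) the joint error was 2.9%, against 3.0% for non-inferiority alone.

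A reader might also infer that the omission lets an analyst choose afterwards across a very wide span of error rates. Much of any such span comes from the randomisation scheme and the between-survey correlation, which no analyst picks.

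It is also fair that distance stratification does not always leave the error at 8%, and that the SAP already plans adjusted analyses with the stratification factor. Adding that factor does not cure the small-sample problem; with an uncorrected sandwich it slightly raises the error. It is proposed here together with the correction, so that the model matches the randomisation.

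**Conclusion.** The point holds as a gap that should be closed. If a standard uncorrected sandwich with a normal cut-off is used, the full-versus-control test runs at about 8% two-sided (about 4% instead of 2.5% favouring vaccine), and its nominal 95% CI covers about 91% to 92%. The no-stratification result does not depend on r. Under distance-stratified randomisation the error stays near 8% on change from baseline if the distance gap is stable between surveys; it can be about 6% if distance also shifts the change and is left out of the model.

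The damage is confined to the superiority test's own level and interval. Point estimates are unbiased, the fixed sequence is sound, and non-inferiority moves only to about 3% one-sided. On follow-up prevalence at the planned 30% v 15%, the gate decision would rarely change.

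**What to change.** In SAP 4.3.2.1, for both primary GEE contrasts:

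1. Name a bias-corrected sandwich and its degrees of freedom. One option is Mancl-DeRouen with t on the clusters in the two arms compared minus the cluster-level parameters (27 + 9 − 2 = 34 for full dose v control without covariates, 33 with distance). The other is Kauermann-Carroll with Satterthwaite df; with equal cluster sizes and no covariates this equals a Welch t-test on cluster values.
2. Include the randomisation stratification factor in the primary model, not only in the adjusted analyses.
3. Reconcile the GEE sentence that names the fractional dose as comparator with the stated full-versus-control test.

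The text change is a few sentences; the statistical cost is precision. The full-versus-control CI widens by about 1 to 2 points each side. For follow-up prevalence with 36 per cluster, the expected half-width goes from 1.96 × √0.001194 = 6.8 points to 2.03 × √0.001471 = 7.8 points.

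At 30% v 15%, power on follow-up prevalence goes from about 99% to 98% with 36 per cluster, still above the planned 90%. On change from baseline it falls from about 83-94% to 75-90% (36 per cluster, r from 0 to 0.8, assumed). With 29 per cluster, corrected power on change is 69.7% to 87.3% as r goes from 0 to 1, against 78.2% to 92.2% uncorrected. Part of the uncorrected power is the inflated error, so the loss is not a reason to leave the estimator open. The steering committee should see these figures when it reviews power after the baseline survey.

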Six months after the mass vaccination campaign, the post- vaccination cross-sectional survey will be implemented. This will be used to estimate community level carriage of VT pneumococcus after a single-dose PCV delivered as full or fractional dose as well as carriage in the clusters that received no vaccination. The survey

Determining whether mass campaigns with fractional dose PCV10 would accelerate herd protection against pneumococcal transmission in Sub-Saharan Africa

will target the same number of children as the baseline survey and will follow the same methodology with the households selected by simple random sampling from the sampling frame.

Sampling will be independent between the two surveys.

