3.2.2 Safety Assessments

The safety outcomes are AE(s) at the injection site occurring within 7 days after vaccination and SAE(s) occurring within 28 days after the vaccination. SAEs from participants in clusters allocated to the control group will be collected during a period of time from the first vaccination date up to 28 days after the last vaccination date performed in clusters allocated to full or fractional dose, in the geographical area sharing the same health center.

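### SAP 4.3.2.1: the GEE sentence for the primary superiority test names the fractional dose instead of control, and the adjusted full-dose-versus-control analyses list covariates that control clusters lack (two vaccination-dated intervals) or that nearly duplicate arm (campaign coverage)

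*Combined protocol and SAP*

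**What the plan says.** SAP 4.3.2.1 opens with "The primary analysis is the test of the superiority of the full dose vaccination arm compared to the control arm". The next sentence says this analysis will use GEE on the intent-to-treat population to estimate risk differences "for the effect of the full dose vaccination on the reduction in VT carriage compared to the fractional dose". Non-inferiority (full minus fractional) has its own GEE sentence further down, so no GEE sentence in the section names control as comparator.

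The same paragraph then says adjusted analyses will be performed with the stratification factor and an open-ended covariate list: age, sex, "vaccination coverage, time between baseline survey and vaccination, time between vaccination and follow-up survey, baseline prevalence of VT carriage". A coverage formula follows, introduced by "The administrative vaccination coverage for each site where vaccination campaign is performed, is obtained by the formula": vaccinees divided by expected children aged 1-9 years.

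Four other places bear on this:

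- SAP 3.1.1 says the follow-up survey measures carriage in both campaign arms "as well as carriage in the clusters that received no vaccination". SAP 3.1.3 adds that controls receive no dummy intervention.
- SAP 3.2.2 (and likewise 3.1.4) gives control clusters a calendar window for safety only: "SAEs from participants in clusters allocated to the control group will be collected during a period of time from the first vaccination date" to 28 days after the last one in the same health-centre area.
- SAP 4.2 treats missing data in general as missing at random, without imputation.
- SAP 4.1 states: "The primary endpoint will be the change from baseline in VT carriage at 6 months post-vaccination campaign". SAP 3.1.1 makes the two surveys independent samples.

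**The concern.** Superiority of full dose over control is the gatekeeper: under SAP 4.3, non-inferiority is tested only if superiority is shown. The sentence giving its model should carry the right contrast.

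Once control is the comparator, three of the listed covariates cause trouble. The two intervals need a vaccination date, which control clusters do not have, and the SAP gives them no reference date for efficacy. Campaign coverage is defined only for campaign sites. Setting it to 0 in controls makes it close to a copy of the arm indicator. It also arises after randomisation and is a means by which the campaign works, so adjusting for it removes part or all of the effect being estimated.

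At stake is an adjusted full-dose-versus-control result that either cannot be fitted or depends on a coding choice made after the data are seen. In the second case it could appear to contradict a real campaign effect.

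**Working it through.** **Inputs from the documents.** 27 full-dose and 9 control clusters, 36 children per cluster, ICC 0.02, VT prevalence 30% without vaccine and 15% after full dose, margin 7.5 points (SAP 3.1.2, 3.1.3). **Assumed, because not given:** mean and between-cluster SD of coverage, and the between-survey correlation of cluster prevalence (rho, 0 to 1).

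**1. The plan's own figures reproduce.** Superiority: 161 children per arm × design effect 1 + 29 × 0.02 = 1.58, divided by 30, is 8.48, so 9 clusters as stated. Non-inferiority: SE = √(2 × 0.15 × 0.85 × 1.70 / 972) = 0.0211, power 94.4% against a stated 90% or more.

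**2. Covariate-free full dose versus control.** On follow-up prevalence, power with 27 against 9 clusters is 99.1%. For the change endpoint, the variance per arm is [between-cluster variance of the change + 0.98 × (sum of pq over both surveys)/36] / clusters. At rho = 0:

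- full dose: (0.00675 + 0.98 × 0.3375/36)/27 = 0.000590
- control: (0.0084 + 0.98 × 0.42/36)/9 = 0.002204
- SE = √0.002794 = 0.0529, power 81.0%

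At rho = 0.5 and 1 the SE is 0.0470 and 0.0402, and power is 89.1% and 96.2%. None of this involves the disputed covariates.

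**3. Either interval, complete cases.** Planned follow-up children fall from 36 × 36 = 1,296 to 27 × 36 = 972, with 0 of 324 controls. Arm then equals the intercept column. With one interval the design has rank 2 of 3; with coverage also left missing and all three terms entered, 4 of 5. With both surveys stacked, 2,592 records fall to 1,944. Arm equals the intercept and arm-by-survey equals survey, so rank is 3 of 5 with one term and 5 of 7 with three. The effect is not estimable. No assumed figure is used, and a smaller number of children per cluster would not change it.

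**4. Coverage coded 0 in controls.** With a fraction 0.75 of clusters in the full-dose arm, the variance inflation factor for arm is 1 + 0.25 × (mean/SD)². If coverage enters the change contrast, the arm coefficient becomes the full-dose line extrapolated to zero coverage minus the control mean. Its variance is the full-dose term of step 2 × (1 + (mean/SD)²) plus the control term. For 60% (SD 20) and rho = 0 this is √(0.000590 × 10 + 0.002204) = 0.090, against 0.093 simulated. Simulation (2,000 runs per scenario, small-sample correction, effect constant at 15 points whatever the coverage) gave:

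| Assumed coverage, mean (SD) | VIF for arm | SD of arm estimate, rho 0 / 1 | Power, rho 0 / 1 |
|---|---|---|---|
| 60% (20) | 3.3 | 0.093 / 0.073 | 35% / 54% |
| 75% (12) | 10.8 | 0.178 / 0.130 | 17% / 23% |
| 90% (5) | 82 | 0.464 / 0.368 | 7% / 9% |

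If the effect acts wholly through coverage, the arm estimate is about 0 instead of -15 points. A follow-up-only GEE (150 runs per setting, assumed mean coverage 85%, SD 5 to 20 points) gave a correlation of 0.99 to 0.93 between coverage and arm. The SE rose 7.3-fold to 2.4-fold, and power was 17% to 49% against 99% to 100% without coverage.

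**5. Where it does no harm.** In the stacked model, zero-coded coverage entered only as a time-constant main effect left the arm-by-survey estimate unchanged (difference below 1e-14). For full versus fractional dose, VIF is 1.01 and simulated non-inferiority power is about 93% with or without coverage.

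**The case against.** **The comparator slip misleads nobody.** The opening sentence of SAP 4.3.2.1, the objective (SAP 2.1), protocol section 12, the sizing (SAP 3.1.2) and the test order (SAP 4.3) all point to control. This stands: a reader might infer that the primary test is really full against fractional dose, and the documents do not support that. It is an editorial correction, but in the model sentence of the gatekeeping test.

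**Read literally, the covariates belong to full versus fractional dose**, where all three are defined. That is fair, and the list may have been drafted with the vaccinated arms in mind. But correcting the comparator then attaches the list to the contrast with control, so both should be settled together.

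**Coverage does have a value in controls.** The formula gives 0 where nobody is vaccinated. This stands, and the case against coverage therefore rests on near-duplication of arm and on the causal pathway. It could instead mean routine coverage, which is collected in every cluster, but the formula that follows favours the campaign reading.

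**Losing all controls is not prescribed.** A value that is inapplicable by design is not missing at random, the safety window could be borrowed to date the intervals, and software dropping every control would be noticed. Also, no single model with all the terms is prescribed. All true. Even so, the SAP does not extend the safety window to efficacy, and one interval is enough to lose the contrast.

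**The power losses are not from the documents.** This stands. They rest on assumed coverage and on coverage entering a follow-up or change contrast, which the SAP does not specify.

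**Conclusion.** The point holds in a limited form. The comparator in the GEE sentence is wrong and should be corrected. In adjusted full-dose-versus-control analyses, either vaccination-dated interval leaves 0 of 9 control clusters on complete cases. Zero-coded campaign coverage turns a follow-up or change-contrast model into one that no longer estimates the campaign effect. The loss of controls follows from the documents' own counts. The inflation factors of 3.3 to 82 and the power of 7% to 54% are illustrations under assumed coverage.

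A reader might go further and infer that the primary superiority test cannot be fitted or is underpowered because of these covariates. The documents do not support that. The GEE sentence carries no covariates, and protocol section 12 mentions adjusted analyses alongside sensitivity analyses. The natural reading is that adjusted analyses are supportive, although the SAP does not label them so. The covariate-free superiority test and the full-versus-fractional non-inferiority test are not affected by these covariates. The gap between 81-96% and 99.1% power in the covariate-free benchmarks reflects the choice between change and follow-up prevalence, a separate matter.

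**What to change.** 1. In the GEE sentence of SAP 4.3.2.1, replace the fractional dose with the control arm as comparator.
2. In adjusted full-dose-versus-control analyses, remove campaign coverage and the two vaccination-dated intervals. Adjust only for variables defined in every arm: age, sex, proximity stratum, cluster baseline VT prevalence and, if timing matters, survey date or the baseline-to-follow-up interval. Report campaign coverage descriptively.

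The cost is SAP wording only, with no new data and no design change. What is given up is a coverage-adjusted estimate against control.

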3.1.2 Sample Size and Power Considerations

The sample size has been calculated to respond to the objective of determining whether community level prevalence of VT pneumococci after a fractional dose PCV mass campaign among children aged 1-9 years is non-

Determining whether mass campaigns with fractional dose PCV10 would accelerate herd protection against pneumococcal transmission in Sub-Saharan Africa

inferior to that seen after a mass campaign among children aged 1-9 years using full dose PCV as well as determining the superiority of a full dose PCV mass campaign compared to no vaccination. Based on NP carriage studies conducted in Sub-Saharan Africa settings and considering an estimated coverage of 3 doses of PCV in children < 12 months of age of 48% in the study area, we estimate the prevalence of VT carriage, among 1-9 year old, to be between 25 and 35% and take the middle value, 30%, as an initial estimate. We assume a 50% reduction in PCV10 VT carriage after vaccination with a full dose and consider the prevalence of VT carriage amongst vaccinated children with a full dose 6 months after the vaccination campaign to be 15%.

Based on information from a study conducted in the area, we consider an intra-cluster correlation coefficient of 0.02. To test the non-inferiority of a mass campaign using fractional doses compared to a mass campaign using full doses, we have chosen a non-inferiority margin of 7.5% to ensure that a campaign with fractional doses provide at least half of the benefits provided by a campaign using full doses. We consider a 2.5% level of significance for a one-sided test and 90% power. With these assumptions, 27 clusters with 36 households sampled per cluster would provide a power of at least 90% (1944 individuals, with 972 in the full dose and 972 in the fractional dose arm). Non-inferiority will be achieved if the lower limit of the 95% confidence interval (CI) around the difference in the proportion of children with VT carriage (full dose group – fractional dose group) is $> -7.5\%$.

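### SAP 4.3.2.1 does not say which GEE model decides superiority and non-inferiority, and leaves the randomisation stratum and baseline prevalence to unranked adjusted analyses with an open covariate list

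*Combined protocol and SAP*

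**What the plan says.** **Randomisation.** SAP 3.1.3: "Randomization will be stratified by proximity to nearest health center", split at 5 km. Baseline VT prevalence may be added as a factor if the trial steering committee so decides, with minimisation if there is more than one stratum. Allocation waits for the baseline survey results.

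**Superiority.** SAP 4.1 defines the primary endpoint as change from baseline. SAP 4.3.2.1 tests superiority of full dose over control on the reduction from baseline, with GEE to account for clustering. No stratum is named. The sentence describing this GEE gives the fractional-dose arm as the comparator, although the stated test is against control.

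**Non-inferiority.** SAP 4.3.2.1: "For the non-inferiority analysis, the 95%CI around the risk difference in the proportion of children with VT carriage" is obtained by GEE and its lower limit is compared with -7.5 points. Neither a stratum nor a baseline term is named.

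**Adjusted analyses.** The same section says that adjusted analyses with a non-exhaustive covariate list, running up to "baseline prevalence of VT carriage) and stratification factor will be performed". The list also contains vaccination coverage and the time from vaccination to follow-up. The coverage formula is defined for sites where a campaign takes place. The SAP does not rank these analyses against the unadjusted ones. Protocol section 12 mentions adjusted analyses together with sensitivity analyses and defers both to the SAP.

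**The concern.** A confirmatory analysis needs one model per test, fixed in advance. Here each test has at least two candidates, and one of them has an open covariate list. Close to -7.5 points, the choice of model could settle the non-inferiority conclusion.

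Neither candidate is satisfactory as written. The unadjusted model ignores the stratification factor and, for non-inferiority, a baseline survey run in all 63 clusters before allocation. The adjusted model as listed includes variables determined after allocation. Coverage has no defined value in control clusters, and those clusters have no campaign date from which to measure an interval, so that model cannot sensibly decide full dose against control.

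The two tests are also on different scales: change from baseline for superiority, follow-up proportion for non-inferiority. Since the two surveys sample independently, that choice affects precision.

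**Working it through.** **Inputs from the documents (SAP 3.1.2).**
- "We consider a 2.5% level of significance for a one-sided test and 90% power"
- "we have chosen a non-inferiority margin of 7.5" points
- Baseline and control prevalence: "take the middle value, 30%, as an initial estimate"
- Full dose: "consider the prevalence of VT carriage amongst vaccinated children with a full dose 6 months after the vaccination campaign to be 15"%; fractional dose taken as equal
- "we consider an intra-cluster correlation coefficient of 0.02"
- 27, 27 and 9 clusters of m = 36 children

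**Assumed.** The correlation c between a cluster's true prevalence in the two surveys is not in the documents. I use 0.5, 0.8 and 1.0. Powers below use the normal approximation.

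**1. The plan's own figure.** Design effect = 1 + 35 × 0.02 = 1.70. SE of full minus fractional = √(2 × 0.15 × 0.85 × 1.70 / 972) = 2.11 points, so the 95% CI half-width is 1.96 × 2.11 = 4.14 points. Power = Φ(7.5/2.11 − 1.96) = 94.4% (93.6% using t with 52 df). The stated 90% or more is reproduced without any adjustment.

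**2. Adding cluster baseline prevalence to the non-inferiority model.** The correlation between observed baseline and follow-up cluster means is r = c × m × ICC / 1.70 = c × 0.72/1.70 = 0.424c. The SE is multiplied by √(1 − r²).

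| c (assumed) | r | Variance reduction | Half-width, points | NI power | Equivalent extra clusters per arm |
|---|---|---|---|---|---|
| no adjustment | – | – | 4.14 | 94.4% | – |
| 0.5 | 0.21 | 4.5% | 4.05 | 95.3% | 1.3 |
| 0.8 | 0.34 | 11.5% | 3.89 | 96.5% | 3.5 |
| 1.0 | 0.42 | 17.9% | 3.75 | 97.5% | 5.9 |

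The last column is 27/(1 − r²) − 27. A cluster-level simulation at c = 0.8 agrees: 93.5% on follow-up alone, 95.5% with baseline as a covariate.

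**3. If the ICC exceeds the plan (assumption: 0.05).** Design effect = 1 + 35 × 0.05 = 2.75, SE = 2.69 points, unadjusted power 79.7%. With adjustment, r = 0.655c and power is 84.0%, 90.6% and 95.8% for c = 0.5, 0.8 and 1.0.

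**4. Superiority as a change score.** Variances per cluster mean:
- follow-up, full dose: 0.1275 × 1.70/36 = 0.00602
- follow-up, control, and baseline in either arm: 0.21 × 1.70/36 = 0.00992

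Follow-up only: SE = √(0.00602/27 + 0.00992/9) = 3.64 points; power = Φ(15/3.64 − 1.96) = 98.5%.

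Change from baseline, with covariance c × ICC × √(product of the two binomial variances):
- full dose, c = 0.5: 0.00602 + 0.00992 − 2 × 0.5 × 0.02 × √(0.1275 × 0.21) = 0.01266
- control, c = 0.5: 2 × 0.00992 − 2 × 0.5 × 0.02 × 0.21 = 0.01563
- SE = √(0.01266/27 + 0.01563/9) = 4.70 points; power 89.1%

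The same steps give 93.6% at c = 0.8 and 96.2% at c = 1.0. With baseline as a covariate instead, power is 98.8%, 99.2% and 99.5%. So at the planned ICC, subtracting an independently sampled baseline costs precision, and adjusting for it does not.

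**5. Distance stratum.** Its gain cannot be computed: the documents give neither stratum sizes nor the share of between-cluster variance that distance explains.

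**The case against.** The other side has good points. The adjusted analyses sit inside the section headed as the primary analysis and are nowhere called secondary. Baseline already enters the superiority test, and allocation is held back so that a significant baseline imbalance can be dealt with by stratification. The planned tests meet their stated power unadjusted. Omitting a stratification factor generally makes inference conservative and does not bias the risk difference. The size of any gain rests on a correlation that the documents do not give. With independent samples, and vaccination between the surveys in 54 of 63 clusters, a low value is plausible.

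All of that stands, and it rules out several stronger readings:
- **That both deciding models leave out baseline.** This fails for superiority, which is defined on reduction from baseline. Only the non-inferiority criterion lacks a baseline term.
- **That the adjusted analyses are settled as side analyses.** Protocol section 12 places them beside sensitivity analyses, but neither document ranks them.
- **That chance imbalance in the 9-cluster control arm goes uncorrected.** That arm matters for superiority, where baseline enters as a change and randomisation may be stratified on it.
- **That the trial is underpowered without adjustment.** At the planned ICC it is not.

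What the objection does not answer is the silence on which model decides, the open list, and the mixing of pre- and post-randomisation covariates.

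**Conclusion.** The point holds as a failure to name the deciding model, with a modest efficiency gain available from naming a better one. At the planned ICC of 0.02 that gain is about 1 to 3 points of non-inferiority power (94.4% to 95.3–97.5%) and a half-width of 4.05–3.75 instead of 4.14 points, for c between 0.5 and 1.0. It becomes material only if the ICC is above the plan: at an assumed 0.05, about 80% rises to 84–96%. The plan takes its ICC from a meningococcal carriage trial in the area (protocol 7.12), so adjustment gives some protection on an uncertain input, but nothing in the documents shows that 0.02 is wrong.

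For superiority the gain is avoiding the loss from an unadjusted change score, whose power of 89.1–96.2% compares with 98.5% for follow-up alone. The lower end falls just under the 90% planned, and only if superiority is analysed in that way and c is near 0.5.

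No bias or inflation of type I error from a single pre-specified model is shown. The risk to validity is the freedom to choose between versions after seeing the data. The change should be made, but the design does not depend on it.

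**What to change.** Amend SAP 4.3.2.1 before unblinded analysis:

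1. Name one deciding model for both tests: a GEE risk difference on 6-month VT carriage with arm, distance stratum, any minimisation factor actually used, and cluster baseline VT prevalence.
2. State that this model decides superiority and then non-inferiority, and keep the unadjusted GEE as a sensitivity analysis.
3. Keep post-randomisation variables (vaccination coverage, time from vaccination to follow-up) out of the deciding model.
4. Delete the qualifier that leaves the covariate list open.
5. Reconcile the change-from-baseline endpoint in SAP 4.1 with this model, and correct the comparator named in the superiority GEE sentence.

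The cost is wording and about two cluster-level degrees of freedom. No extra clusters, children or data items are needed, since the plan already provides for both surveys and for the distance classification. A reader might infer that the data are already in hand, but the protocol synopsis gives the trial as not yet recruiting.
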